LIST OF ABBREVIATIONS

Abbreviation	Explanation
AI	Artificial Intelligence
AUROC	Area Under the Receiver Operating Characteristic
BSI	British Standards Institution
CI	Chief Investigator
CONSORT	Consolidated Standards of Reporting Trials
DCS	Department of Computer Science
EPR	Electronic Patient Record
GCP	Good Clinical Practice
H&E	Haematoxylin and Eosin
HRA	Health Research Authority
IRAS	Integrated Research Application System
iQC	Image Quality Control
ISRCTN	International Standard Randomised Controlled Trial Number
IVD-CE	In Vitro Diagnostic - Conformité Européene (European Conformity)
MHRA	Medicines and Healthcare products Regulatory Agency
MRC	Medical Research Council
NPV	Negative Predictive Value
PI	Principal Investigator
PPI	Patient & Public Involvement
PPV	Positive Predictive Value
REC	Research Ethics Committee
R&D	Research and Development
SMG	Study Management Group
SOP	Standard Operating Procedure
SSC	Study Steering Committee
TIA	Tissue Image Analytics
UHCW	University Hospital Coventry and Warwickshire
UK-CA	United Kingdom Conformity Assessed
UoW	University of Warwick
WCTU	Warwick Clinical Trials Unit
WSI	Whole-Slide Image

GLOSSARY

Term	Definition
Case	The whole case belonging to a patient, this may contain one or more specimens.
Specimen	A piece of tissue taken from specific part of the large bowel. The separate specimens taken from that patient form the case (e.g., often multiple biopsies are taken from different parts of the colon in a single case). The terms sample, specimen and biopsy all mean the same thing.
Slide	The specific slides produced from each specimen/specimens. Each specimen may be split into/ produce several slides (for example large specimens or if a pathologist has requested multiple levels), or multiple specimens may be placed on a single slide. The diagnosis of a specimen issued in the clinical report at each trust.
Reference diagnosis	The study pathologist's diagnosis at time of recruitment. This is considered the gold standard for algorithm comparison.
COBix diagnosis	The diagnosis given by COBix.
Ground truth diagnosis	The final diagnosis given to cases where there was discrepancy between the reference diagnosis and COBix diagnosis, following consensus review of the case.

1. STUDY SUMMARY SCHEMA

Main study

Design: A multi-centre study comparing classification resulting from COBix algorithm with pathologists' reporting of colon biopsy specimens.

Enrolment: 11,000 cases will be enrolled from 11 participating NHS sites (1,000 cases per site).

Primary objective: Comparing classification of normal/ abnormal categories.

Secondary objectives: Comparing classification of into neoplastic urgent/ neoplastic non-urgent/ non-neoplastic urgent/ non-neoplastic non-urgent categories.

Data analysis: Validation of the COBix algorithm by comparing COBix and pathologists' classifications of the same specimens.

Sub study

Health economics: To assess the impact of COBIX algorithm on workflow productivity.

2. PLAIN ENGLISH SUMMARY

The colon (also called the large bowel) is part of our digestive system or gut. Sometimes diseases can form in the colon – for example colitis, Crohn's disease, and cancer. These can be serious and usually need to be treated.

Diseases are usually diagnosed by taking a sample of tissue (a biopsy) from the colon and having a pathologist (a doctor trained to examine tissue) look at it under a microscope. The pathologist can say whether a sample looks normal (healthy) or not.

Currently, around one third of these samples turn out to be normal. We are looking at ways of checking samples more efficiently whilst making sure we don't miss any which have disease and need treating.

New technologies using computer programmes (algorithms) are very promising. The one we are looking at in this study is called COBix. In a previous study, the algorithm has been developed on thousands of colon samples and has been shown to be highly accurate.

We now need to test COBix even more to make sure it is accurate wherever it is used, as every hospital has slightly different equipment and different ways of working.

For this study we plan to look at 11,000 colon cases from 11 different hospital trusts. For each one we will compare the COBlx result with the findings of a pathologist.

We want to find out whether COBlx is accurate and can be used safely in the future to allow patients to be diagnosed more quickly and safely.

3. BACKGROUND & RATIONALE

Histopathological diagnosis is a pivotal step in the diagnosis and treatment pathways of many major diseases. It provides the key diagnostic information and myriad characteristics of the diseased tissue important for deciding the future management plan. Advances, particularly around screening for early detection of cancer and improved life expectancy, are placing additional burden on already overstretched Cellular Pathology resources within the NHS. Early stage disease is more difficult to detect leading to more challenging and often increased numbers of biopsies and more data from these biopsies is needed to provide the best standard of care. In Cellular Pathology, 32% of consultants are over 55 and most of them expected to retire in 5 years; the number of new consultants is less than half the number expected to retire; 55% of the histopathology departments surveyed hold vacancies^{1,2}. The result is escalating pressure on Cellular Pathology testing capacity (Figure 1), contributing to delays to diagnosis of cancer and other disease which worsens outcomes for patients³. Endoscopic biopsies from the large bowel account for 17.8% of the requests in NHS cellular pathology laboratories. Of these biopsies, 34.5% are reported as normal (Table 1). For normal slides, the pathologist contributes minimally to the care of the patient. Yet the scrutiny of the slides to deliver this verdict remains similar to slides containing disease, where the pathologist's expertise is crucial in guiding the clinical team on how to treat the patient.

Site	Histopathology requests	Large bowel biopsies (%)	Large bowel biopsies normal (%)
Coventry	41,771	4,877 (11.7)	1,680 (34.4)
Wolverhampton	52,008	9,708 (18.7)	4,140 (42.6)
Oxford	56,575	7,766 (13.7)	3,938 (50.7)
Nottingham	59,851	10,562 (17.6)	3,428 (32.4)
Newcastle	59,843	5,348 (8.9)	2,015 (37.7)
Durham	34,958	6,240 (17.8)	2,353 (37.7)
Glasgow	108,000	29,000 (13.9)	7,830 (27)
Total	413,006	73,501 (17.8)	25,384 (34.5)

Table 1 The numbers of colon and rectal biopsies performed in 2019 in comparison to overall workload. The proportion of biopsies reported as normal varies between sites ranging between 27 and 50.7%, the mean value is 34.5%.

Digital pathology systems^{4,5} are recognised as important in addressing these problems and allow Artificial Intelligence (AI) tools to revolutionise delivery of Cellular Pathology^{1,6-8}. Transition to digital pathology across the UK has been accelerated during the COVID-19 pandemic⁹. However, use of AI is limited and there is no existing AI addressing the screening of large bowel biopsies. The colon and rectal biopsy (COBI) tool is an exemplar project of the Industrial Strategy Challenge Fund centre of excellence PathLAKE¹⁰, designed to efficiently and accurately screen normal colon biopsies in order to address this unmet need.

4. STUDY DESIGN

4.1 Aims and Objectives

The reporting and diagnosis of endoscopic large bowel biopsies in the United Kingdom is currently performed manually, mostly by consultant pathologists. This proposal aims to use AI pre-screening of slides to reduce workload and improve workflow. The colon and rectal biopsy reporting AI tool (COBix) screens digitised whole-slide images (WSIs) of Haematoxylin and Eosin (H&E) stained biopsies sorting them into five groups: normal, abnormal neoplastic urgent, abnormal neoplastic non-urgent, abnormal non-neoplastic urgent and abnormal non-neoplastic non-urgent.

The proposal is to use this tool to remove normal slides from the pathologists' workload and to triage abnormal cases into urgent and non-urgent groups depending on the severity of disease detected. This will allow pathologists to focus on abnormal specimens, meaning patients with potentially serious disease are prioritised for immediate review. This should facilitate quicker diagnostic reporting, with greater priority given to serious disease, leading to faster treatment decisions. This helps deliver the aims of the NHS Long Term Plan¹⁴ to diagnose cancer earlier and to support pathologists, clinicians, and patients by concentrating health resources on those patients that require treatment.

COBI has been developed as part of the PathLAKE project. The algorithm has been trained on ~3,400 WSIs and tested on 1,700 unseen slides delivering an area under receiver operating characteristic curve (AUROC) value of 0.96-0.99. These results demonstrate highly effective segregation of slides into three categories (normal, abnormal neoplastic, abnormal non-neoplastic), with high sensitivity and negative predictive values comparable to human pathologists. COBix, the next iteration which includes individual cell recognition is now being introduced to deliver greater accuracy for the identification of non-neoplastic disease and triaging of cases into urgent and non-urgent categories. We have made careful provision for IVD-CE and UK-CA clearance, sharing with BSI and the MHRA our approach to the development of this tool. The multi-site study outlined in this protocol will provide the efficacy and safety data needed for regulatory approval, as well as key health economic data indicating the impact the technology will have in routine practice.

4.2 The COBix Algorithm Version 1.0

[figure not shown]

Figure 1 Overview of the COBix algorithm for large bowel endoscopic biopsies.

Scanned WSIs of the biopsies are pre-screened by the COBix algorithm which divides the biopsies into normal and abnormal outcome baskets. Abnormal biopsies are triaged into urgent and non-urgent groups depending on the pathology identified. Biopsies with a normal result trigger an automated report of normal tissue. These specimens would not be examined by the pathologist except at the request of the clinician or for quality assurance purposes.

The COBix algorithm (Figure 1) is an in-vitro diagnostic medical device (computer software), intended for use on endoscopic large bowel biopsies from adult patients (over 18 years old) to screen normal from abnormal biopsies and assist in the triage of cases with serious disease for urgent pathologist review. Screening for normal is intended to provide a means of automated reporting of these specimens.

COBix combines two parallel strands of AI technology: **(a)** Hover-Net, the state-of-the-art deep learning model providing individual cell recognition^{11,12}, and **(b)** iterative-draw-and-rank-sampling (IDARS) algorithm, a weakly supervised deep learning strategy recently published in The Lancet Digital Health¹³, for the detection of colorectal carcinoma from routine H&E slides. Combining these algorithms predicts normal and the presence of neoplastic disease, invasive carcinoma and areas of acute inflammation and confidence levels for these predictions. The tool operates on digitised WSIs of colon biopsy slides stained with H&E.

[figure not shown]
[figure not shown]
A**B**

Figure 2 Results of the COBI algorithm based on IDARS a weakly supervised algorithm developed from slide deep learning of data with just the slide level diagnosis.

As shown in Figure 2A, there is excellent detection of neoplastic lesions by the algorithm, but detection of inflammatory conditions is less strong. Figure 2B shows the H&E image of a hyperplastic polyp with a corresponding heat map of the abnormality detected by the algorithm. (IDARS stands for iterative draw and rank sampling which is the approach taken to select informative patches in the training sets used in the algorithm development).

The PathLAKE project has created the prototype, on a dataset of over 8,000 WSIs of large bowel biopsies, with slide level diagnosis on 5,107 slides, divided into training and test sets (60% and 40% respectively). Using the IDARS algorithm alone at x5 magnification equivalent images, and hence only architectural morphological features, we have already achieved excellent separation of normal from neoplastic lesions and abnormal, both neoplastic and non-neoplastic lesions (see Figure 2).

Pathologist ground truth data, in triplicate on 150 selected slides has generated over 250,000 annotations that have been processed and added to the original model of Hover-Net¹¹ (see Figure 3). This is the largest dataset for nuclear instance segmentation in existence, with nearly half a million labelled nuclei in colon tissue¹² (Figure 3).

[figure not shown]

Figure 3 Selected fields of region and cell level annotation made by the Iguana algorithm which has been developed using pathologists' annotation of diagnostic regions and patched of cell level annotation in the training set of slides.

4.3 Medical device classification

COBix is intended to recognise large bowel biopsies as normal or abnormal. It is intended that recognition of normal cases will generate an automated report. This report is designed to be posted onto the electronic patient record (EPR) and communicated to the patient, potentially using the NHS app on mobile devices. It is intended that abnormal cases will remain in the pathologist reporting workflow with annotations visible to the pathologist identifying the regions of interest (ROI) recorded as abnormal. COBix will be classified as a class IIb device under Regulation (EU) 2017/745 Rule 11.

4.4 The Multi-site validation study outline

The study aims to recruit 11,000 patient cases from adults across 11 separate centres in the UK. All the H&E stained slides (from approximately 33,000 specimens) from these cases will be scanned (or in some cases, have already been scanned) to digital WSIs at the recruiting site using equipment used for routine diagnosis. Scanned images will be anonymised and transferred electronically to a storage housed within the TIA Centre. Once these digital slides have been transferred, they will be processed through the COBix algorithm and classified into one of the three main categories and four subcategories. The results of the algorithm classification will be compared to the reference pathologist diagnosis.

4.5 Study size, case selection and case enrolment

The study will enrol 11,000 cases. Sample size for the analysis corresponds to the number of specimens and on average, it is expected that each case will have three specimens. In assessing sample size adequacy, we were conservative assuming that there will be one specimen per case, rather than the expected average of three per case. A sample size of 11,000 is adequate to estimate diagnostic measures (sensitivity, specificity, negative predictive value (NPV) and positive predictive value (PPV)) with high precision if the study will have a positive finding of obtaining sensitivity and NPV values of at least 0.98. Assuming we will observe NPV=0.98 and same number of normal cases by pathologists and COBix algorithm, varying prevalence between 49% and 90% (observed data in seven sites in Table 1), the largest margin of error (1.96 x standard error) for any of the four diagnostic measures is 0.02 so that confidence intervals for all diagnostic measures will be very narrow. This sample size may seem large, but it is essential to deliver comprehensive assessment of the tool across all patient groups and the full range of pathological entities encountered in practice.

The study has been designed with the majority of cases (9,900) coming from retrospective cases, with 1,100 cases being recruited prospectively. Using retrospective cases is appropriate in this setting and ensures the volume of cases can be recruited and examined in the time available. It also ensures rare and unusual entities can be included so we can explore how these are handled by the algorithm. Prospectively recruited cases will be selected sequentially and will allow the study to collect health economics data, including the time taken for pathologists to examine normal biopsies and the broader impact on pathology workflow.

Selected cases are recruited and the specimen reviewed by the study pathologist for enrollment. The specimens are anonymised at the point of enrollment. The anonymisation process provides a unique case number, a part identifier, a block identifier and a slide identifying number. Where multiple specimens are combined into one block and all appear on one slide the process for anonymization and number is the same, but the slide receives multiple numbers to account for each specimen it contains. The fact that it is a multi-specimen slide is annotated in the study database. The orientation of the WSI will be used to segment the WSI into the component parts prior to the slide being processed through COBix.

At the point of review, the study pathologist provides the diagnosis of each specimen in the case under the anonymized number on the study database. This is the **reference classification and diagnosis**. All cases are therefore enrolled with two pathologist reviews: the reporting pathologist and the study pathologist. These may be the same person. The timings for the health economics study are taken on the first review only.

To ensure representation from all ethnic groups, case selection will be divided between racial groups in the following proportions:

- White Caucasian groups 70%;
- Black, Asian and minority ethnic (BAME) groups, including racial group unknown 30%.

Prospective cases

Each site enrolls one hundred sequential large bowel biopsy cases prospectively after the study starts.

Retrospective cases

Nine hundred cases are enrolled from the pathology archives at each site. Of these 100 cases is reserved for the categories of rare and unusual diagnoses. The remaining 800 cases are collected sequentially from a time period chosen by the enrolling site.

Classification of specimens

At enrolment, each specimen is classified by the recruiting pathologist into one of the categories shown below:

Diagnostic categories

- 1) **Normal** (any specimen which contains no evidence of disease)
- 2) **Non-neoplastic non-urgent** (any non-neoplastic abnormality which does not have acute inflammation - necrosis or ulceration)
- 3) **Non-neoplastic urgent** (any non-neoplastic abnormality which includes either acute inflammation or necrosis or ulceration)
- 4) **Neoplastic – non-urgent** (any neoplastic lesion which does not include either invasive carcinoma or other form of malignancy or high-grade dysplasia)
- 5) **Neoplastic urgent** (any neoplastic lesion which includes either high grade dysplasia or invasive carcinoma or other malignant diagnosis)

These categories match then the classification tree in figure 4.

All H&E slides from a case will be seen by the algorithm, but diagnostic categorisation will be done at the specimen level within a case.

[figure not shown]

Figure 4 is a schematic diagram of the COBIx biopsy classification tree depicting how specimens will be classified in the study.

Both pathologists and COBIx classifies each specimen enrolled into one of the five diagnostic categories shown.

Case selection

Each site collects 1000 cases for the study in the following manner:

First, a search of the pathology archive for any of the diagnoses of interest (Cases of interest) listed below of any age and as many of these cases as can be found number X.

Second, a series of cases 900-X from any time period prior to August 2023 using an enrichment process to ensure 30% of cases come from minority ethnic groups, remaining cases are collected sequentially.

Third, a series of 100 cases collected during the trial period to be arranged with the coordinating centre.

Cases of interest, and other interesting and educational cases discovered during the course of the study, will be configured into a training set for the RCPATH Portal.

For the cases enrolled into this study the site will review and ascertain the diagnosis of each specimen and categorise this into one of the 5 categories using the definitions provided.

This work is to be supervised by the principal investigator for the site, the work may be delegate to other staff (trainee pathologists, biomedical scientists, medical students etc. providing they have sufficient training and knowledge and are adequately supervised in this work) as appropriate.

Inclusion criteria

Large bowel endoscopic biopsies from adult patients (over 18 years)

Exclusion criteria

Specimens which are not from large bowel endoscopic biopsies

Incomplete cases with lost slides

Cases from person opting out via the NHS Data opt-out scheme

Faded or damaged slides

Incomplete or missing meta data

The following metadata is required for each case:

Site code

Laboratory number

Ethnic group

Gender

Age group

Procedure type

Tissue Type

Date of biopsy

Colonoscopy report

Clinical details

Specimen parts

Specimen blocks

Macroscopic report

Microscopic report

Diagnosis

SNOMED Code

Scanner type

Image resolution

Table 2 Metadata required for each case

Consensus review of discrepant samples

Where there is a discrepancy between the algorithm diagnostic category and pathologist diagnostic category the case will be reviewed by the consensus review team. A minimum of 3 pathologists will decide the correct or ground truth diagnostic category for each slide in the discrepant sample.

Diagnostic categories

- 1 **Normal** (any sample which contains no evidence of disease)
- 2 **Non-neoplastic – non-urgent** (any non-neoplastic abnormality which does not have acute inflammation - necrosis or ulceration)
- 3 **Non-neoplastic urgent** (any non-neoplastic abnormality which includes either acute inflammation or necrosis or ulceration)
- 4 **Neoplastic – non-urgent** (any neoplastic lesion which does not include either invasive carcinoma other form of malignancy or high-grade dysplasia)
- 5 **Neoplastic urgent** (any neoplastic lesion which includes either high grade dysplasia or invasive carcinoma or other malignant diagnosis).

Rare entities sought for enrichment:

Entity	Relevant SNOMED codes
Pseudolipomatosis	Not found
Pouchitis	Not found
Diversion colitis	Not found
Eosinophilic colitis	D5-41712, M-430401
Infectious aetiologies	-
Yersinia	L-1E400
Pseudomembranous C difficile colitis	L-14137, M-417801
Protozoan infections (amoebic colitis)	DE-50090, L-50001, L-515001
Histoplasmosis	DE-40700
Cryptosporidium	L-52400
Cytomegalovirus	L-36500, DE-32610
Adenovirus	L-35800
Mycobacterium avium complex	L-21815
Mycobacterium tuberculosis	L-21907
HIV associated giant cells	L-352101
Malakoplakia	M-44170, D5-44360, D5-45380
Parasites (e.g. T trichiura, E vermicularis, schistosomiasis, strongloidiasis)	L-50000, L-550001, L-56600, L-56601, L-55300, L-58120
Ischaemic colitis	F-39340, D5-41210
Vasculitis	D3-80650

Amyloidosis	M-97691,M-551002, D6-94500
Mastocytosis	M-97401
Langerhans cell histiocytosis	M-97513, D6-64952, M-97511, M-77870
Radiation colitis	M-11600, DD-64100, M-11620
Graph versus host disease	DC-50050
Diverticular disease associated colitis	M-40630, D5-43220, D5-43210, D5-43204
Mucosal prolapse conditions	-
Solitary rectal ulcer syndrome	Not found (D5-45420 = ulcer of rectum)
Inflammatory cloacogenic polyp	Not found
Diverticular disease associated polyps (polypoid prolapsing mucosal folds)	Not found
Cap polyposis	Not found
Juvenile polyps (sporadic and syndromic)	M-75662
Peutz-Jeghers polyps	M-75660
Endometriosis	M-76500
Colonic xanthoma	M-553002
Gastric heterotopia	M-00370, M-260004 (both non specific heterotopia)
Pulse granuloma	Not found (M-44002 - granuloma NOS)
Mucosal pneumatosis/ Pneumatosis cystoides intestinalis	D5-43320, M-333801
Leiomyoma	M-88900
Neural tumours including	-
Ganglioneuroma	M-94900
Neurofibroma	M-95400
Benign fibroblastic polyps/ perineuroma	M-95710
Mucosal schwann cell hamartoma	Not found
Benign epithelioid nerve sheath tumours/ epithelioid schwannoma	M-95600, M-956005
Neuroma	M-95700
Granular cell tumour	M-95800
Lipoma	M-88500
Vascular tumours including	-
Haemangioma	M-91200
Lymphangioma	M-91700
Kaposi sarcoma	M-91403, D3-F0843
Angiosarcoma	M-91203, M-912031
Gastrointestinal stromal tumour	M-89363, M-89361
Signet ring cell carcinoma	M-62140, M-849031, M-84903, M-84906
Metastatic malignancy NOS	M-80006
Metastatic adenocarcinoma	M-81406
Metastatic melanoma	M-87206
Metastatic sarcoma	M-88003
Metastatic SCC	M-80706
Lymphoma	M-95903, M-96993, M-95913, M-97023
Neuroendocrine tumours (of all types)	M-82403, M-80413, M-80133

Table 3 Rare entities sought for enrichment

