6. STATISTICAL ANALYSIS

The aim of the study is to validate the COBix diagnostic tool that will be developed before the study begins. We will compute diagnostic measures of sensitivity, specificity, positive predictive value (PPV) and negative predictive value (NPV). The gold standard in the analysis is a pathologist's reference diagnosis. A positive result will be the ability of the COBix diagnostic tool to screen out normal cases. For patient safety, the desire is for the tool to achieve this whilst minimising false negatives and so very high sensitivity and very high NPV are desired. NPV is a function of prevalence of abnormal cases. The prevalence in the study will not be representative because there will be enriching for rare cases (e.g., by ethnicity). However, very high NPV is desired for any case mix. COBix will be considered a good tool if sensitivity and NPV are above 0.98. Specificity will quantify the proportion of normal cases that are screened out and hence the saving in pathologists' workload.

For the cases that are abnormal on both the COBix algorithm and reference diagnosis, based on the categorisation "neoplastic" and "non-neoplastic", we will compute kappa statistic. We will use the kappa statistic to assess agreement between COBix and pathologist diagnosis in categorising abnormal cases as neoplastic or non-neoplastic. Also, taking the gold standard as a pathologist's categorisation of an abnormal case as neoplastic or non-neoplastic, we will compute sensitivity, specificity, and other diagnostic measures.

For the cases that are abnormal on both the COBix algorithm and reference diagnosis, based on the categorisation "urgent" and "non-urgent", we will compute kappa statistic. We will use this kappa statistic to assess agreement between COBix and pathologist diagnosis in categorising an abnormal case as urgent or non-urgent. Also, taking a pathologist's reference diagnoses as the gold standard, we will compute sensitivity, specificity, and other diagnostic measures. Comparison of categorisation as urgent and non-urgent will be based on all abnormal cases and in subgroup analyses of separately analysing neoplastic cases and non-neoplastic cases.

Subgroup analysis will repeat the above set of analyses for clinically important patient subgroups such as categories based on sex, ethnicity, age and site of the biopsy.

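### The margin of error of 0.02 behind the 11,000 cases does not follow from its stated inputs (they give 0.008), and the 90% prevalence is not in Table 1

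*Protocol*

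**What the plan says.** Protocol section 4.5 gives the precision argument in one paragraph. It opens with the claim that "A sample size of 11,000 is adequate to estimate diagnostic measures", on the condition that sensitivity and NPV come out at 0.98 or higher. Its inputs are:

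- **Unit and number:** 11,000 specimens, because "we were conservative assuming that there will be one specimen per case, rather than the expected average of three per case".
- **Accuracy:** "Assuming we will observe NPV=0.98 and same number of normal cases by pathologists and COBix algorithm".
- **Prevalence:** "varying prevalence between 49% and 90% (observed data in seven sites in Table 1").
- **Result:** "the largest margin of error (1.96 x standard error) for any of the four diagnostic measures is 0.02", from which the paragraph concludes that the intervals for all four measures will be very narrow.

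The caption of Table 1 in section 3 says that the proportion of biopsies "reported as normal varies between sites ranging between 27 and 50.7" percent. Section 6 fixes what prevalence means: "NPV is a function of prevalence of abnormal cases".

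**The concern.** The paragraph states every input needed to recompute its result, and the result does not come out. The prevalence range is also presented as observed data, but its upper end cannot be found in the table cited for it.

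This is the only numerical argument for the study size. A reader who wants to know how precisely the study will measure NPV and specificity, for a tool judged against 0.98 on sensitivity and NPV (section 6), is given a figure that the inputs do not produce. The assumption of equal normals also fixes specificity at 0.98. The paragraph does not say so, although specificity is the measure that section 6 uses for the saving in pathologists' workload.

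**Working it through.** **Inputs (section 4.5).** N = 11,000; NPV = 0.98; the same number of normals by both readers; prevalence of abnormal p from 0.49 to 0.90; margin = 1.96 × standard error. The standard error is taken as the simple binomial one, since no other is mentioned.

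**Step 1: the implied 2×2 table.** Normals by the algorithm are TN + FN and normals by the pathologist are TN + FP. If these are equal, FP = FN. Hence:

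- normals by either reader = N(1 − p), and FN = FP = 0.02 × N(1 − p)
- specificity = NPV = 0.98, with denominator N(1 − p)
- sensitivity = PPV = 1 − 0.02(1 − p)/p, with denominator Np

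**Step 2: margins, 1.96 × √(q(1 − q)/n).**

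| Prevalence | Normals | Specificity = NPV | Margin | Sensitivity = PPV | Margin |
|---|---|---|---|---|---|
| 49% | 5,610 | 0.98 | 0.0037 | 0.979 | 0.0038 |
| 73% | 2,970 | 0.98 | 0.0050 | 0.993 | 0.0019 |
| 90% | 1,100 | 0.98 | 0.0083 | 0.998 | 0.0009 |

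At 90%: 1.96 × √(0.0196/1,100) = 0.0083. This is the maximum over 49% to 90%. The stated 0.02 is about 2.4 times as large (0.02/0.0083). Rounding does not explain the gap, since 0.0083 rounds to 0.01. Under these inputs a margin of 0.02 at 90% prevalence needs only about 1,883 specimens.

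**Step 3: can 0.02 be recovered some other way?** Several readings come near it, but each breaks something the paragraph states.

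- Reading 90% as the share of normals gives 0.0227, with sensitivity 0.82.
- Fixing sensitivity rather than NPV at 0.98, with equal normals at 90% abnormal, gives 0.0227, with NPV 0.82.
- Setting sensitivity and specificity both to 0.98 at 90% gives 0.0199 for NPV, but NPV is then 0.845.
- One site's 1,000 cases at 73% give 0.0167, which is not the stated N.
- The full interval width at 90% is 0.0165, which is not the quantity defined.
- Clustering would need a design effect of (0.02/0.00827)² ≈ 5.8, and none is stated.

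**Step 4: the prevalence range.** The abnormal share in Table 1 is 100% minus the normal share: Coventry 65.6%, Wolverhampton 57.4%, Oxford 49.3%, Nottingham 67.6% (67.5% from the counts), Newcastle 62.3%, Durham 62.3%, Glasgow 73.0%. The lower end of 49% matches Oxford. The upper end is 73%, not 90%.

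Enrichment is not given as the source of the 90%. If the 100 retrospective cases per site reserved for rare diagnoses were all abnormal, the highest site would rise only to 0.10 + 0.90 × 0.73 = 0.757. The case-selection text in section 4.5 leaves the number of rare cases open, so heavier enrichment is possible, but that would be an assumption and not Table 1 data.

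**Step 5: what changes if specificity is not 0.98.** The protocol gives no specificity, so 0.5 to 0.9 is an assumed range. Keep NPV at 0.98 and drop equal normals. With specificity s, its margin is 1.96 × √(s(1 − s)/(N(1 − p))), and the number called normal by the algorithm is N(1 − p)s/0.98.

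| Prevalence | Specificity (assumed) | Specificity margin | NPV margin |
|---|---|---|---|
| 49% | 0.9 | 0.0079 | 0.0038 |
| 49% | 0.5 | 0.0131 | 0.0051 |
| 73% | 0.9 | 0.0108 | 0.0053 |
| 73% | 0.5 | 0.0180 | 0.0070 |

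Over 49% to 73%, the specificity margin is therefore about 0.008 to 0.018 and the NPV margin about 0.004 to 0.007.

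**The case against.** The strongest reply is that the error is harmless. The correct figure is smaller than the stated one, so narrow intervals follow all the more, and nothing else in the protocol depends on 0.02. That stands, and it is why the point is minor.

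It can also be said that the assumption of equal normals is openly stated ("same number of normal cases by pathologists and" the algorithm) and belongs to a scenario in which the study succeeds. That stands too: only its consequence for specificity is left unsaid.

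A reader might infer more than the documents support:

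- **That 0.02 is too small.** At 90% prevalence the specificity margin would pass 0.02 once specificity fell below about 0.87 (0.0236 at 0.80). This needs a prevalence that Table 1 does not show and specificities that the protocol does not give. Over 49% to 73% the specificity margin cannot exceed 0.018 at any specificity.
- **That NPV would be known only to within 0.96 to 1.00.** The protocol gives 0.02 as the largest margin among four measures, not as the margin for NPV.
- **That the size has no other basis.** The same paragraph also appeals to coverage of all patient groups and of the range of pathology.
- **That between-site variation, or a rule for a lower confidence limit to clear 0.98, is missing.** Section 6 asks only that sensitivity and NPV be above 0.98, and such detail may properly sit in the SAP.

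**Conclusion.** The point holds as a minor error with two parts. First, the stated inputs give a largest margin of 0.0083, not 0.02. Second, the 90% prevalence is wrongly attributed to Table 1, which supports 49.3% to 73.0% abnormal; over that range the largest margin is 0.0050.

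These figures rest on simple binomial standard errors, one specimen per case, and prevalence meaning abnormal, as section 6 uses it. Under the stated inputs the published figure is cautious, so the size of 11,000 and the conclusion about narrow intervals are unaffected. It would be wrong to read this as evidence that the study is too small.

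**What to change.** Reword the precision paragraph in section 4.5:

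1. Give the prevalence observed in Table 1 as 49% to 73% abnormal. If a wider range is wanted, for example to allow for enrichment, label it as an assumption.
2. Replace 0.02 with the margin that the inputs produce: 0.005 over 49% to 73%, or 0.008 if 90% is kept.
3. State that equal numbers of normals imply a specificity of 0.98.
4. Show, as labelled assumptions, the margins at lower specificity. For specificity 0.5 to 0.9 over 49% to 73% prevalence, these are about 0.008 to 0.018 for specificity and about 0.004 to 0.007 for NPV.

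The cost is the rewording of one paragraph. The sample size, case selection and analysis do not change.
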